6.3 Protocol Deviations

Protocol deviations will be reviewed, assessed, and documented by sponsor personnel before database lock.

The number and percentage of subjects with one or more major protocol deviations will be tabulated by treatment for the Safety Population.

All protocol deviations will be listed for the Enrolled Population.

6.4 Demographic and Baseline Characteristics

Subjects' demographic and baseline characteristics will be summarized by treatment sequence, and will include:

- Age at screening (years; if not reported, age will be calculated as integer of [(year of informed consent signed – year of birth)/365.25]
- Sex
- Ethnicity
- Race
- Height (cm)
- Weight (kg)
- BMI (kg/m²)

Demographics and baseline characteristics will be listed for the Safety Population.

6.5 Medical, Surgical, and Social History

Medical, surgical, and social history will be coded using the Medical Dictionary for Regulatory Activities (MedDRA) version 21.1 or higher.

The frequency count and percentage of patients experiencing any medical conditions will be tabulated by system organ classifications (SOC) and preferred term (PT) for treatment sequence. If a preferred term or system organ class was reported more than once for a subject, the subject will be counted once in the incidence for that preferred term or system organ class.

Medical, surgical, and social history data will be listed for the Safety Population.

6.6 Prior and Concomitant Medications

All medications will be coded according to the WHO drug dictionary which includes the WHO Drug Preferred Name and the ATC Classification Level 2 and 4.

Prior medications are medications taken prior to first dose of the study drug.

Concomitant medications are medications being taken on or after first dose of study drug. Medications taken prior to first dose date and were ongoing on the date of the first dose will be considered concomitant medications. Medications with missing end dates are assumed to be concomitant medications.

Prior medications will be summarized by ATC Level 2 and preferred term (ATC Level 4) by treatment sequence. Concomitant medications will be summarized by treatment. If an ATC Level 2 or Level 4 term was reported more than once for a subject, the subject will be counted once in the incidence for that term.

Prior and concomitant medications will be listed for the Safety Population.

7. Safety Analysis

7.1 Extent of Study Drug Exposure

Exposure to study drug (ADX-629, placebo) in the treatment/post-treatment periods (Visit 3, Treatment period 1, Post-Treatment Period 1 (Visits 4a and 4b), Treatment Period 2, Post-Treatment Period 2 (Visits 5a and 5b)) will be summarized by treatment for the Safety Population, and will include:

- Total number of days on treatment
- Total number of tablets taken
- Compliance (%), defined as total number of doses taken/planned total number of doses taken x100
- Compliance category: < 80%, ≥ 80% - ≤125%, > 125%

Exposure to study drug will be listed for the Safety Population.

7.2 Adverse Events

AEs will be coded using the Medical Dictionary for Regulatory Activities (MedDRA) coding dictionary (Version 20.0 or higher) preferred term (PT) and system organ classification (SOC).

An AE will be considered treatment emergent (TEAE) if it begins or worsens in severity after the first dose of the study drug in Treatment Period 1.

All TEAEs with start dates prior to first dose date of Treatment Period 2 will be classified as AEs that occurred in Treatment/Post-Treatment Period 1.

TEAEs are classified as related and not related to the study drug. Any TEAEs with missing relationship to study drug will be considered related to study drug.

An overall summary for number of subjects with events in each treatment will be provided, and will include:

- Any TEAE
- Any drug-related TEAE
- Any serious TEAE
- Any TEAE leading to study drug discontinuation

The following types of summaries for each treatment will be provided. Summaries will be sorted by decreasing frequency of PT within SOC, which will be sorted alphabetically, and will include:

- TEAEs by SOC and PT
- Drug-Related TEAEs by SOC and PT
- Serious TEAEs by SOC and PT
- TEAEs by SOC, PT, and maximum Severity

- TEAEs leading to study drug discontinuation by SOC and PT

If a PT or SOC was reported more than once for a subject, the subject will be counted once in the incidence for that PT or SOC.

In the tabulation of TEAE by severity, only the most severe PT or SOC for each subject will be included. Missing severity will be counted as Severe.

In the summary of drug-related TEAEs, only the strongest relationship will be included.

Listings will be provided including for Safety Population, and will include:

- All AEs
- Serious TEAEs
- TEAEs leading to study drug discontinuation

7.3 Clinical Laboratory Tests

Chemistry (complete blood count [CBC] with differential), hematology, and urinalysis laboratory tests are performed at the Medical Screening Visit and within 3 days prior to the first dose of study drug. Additional tests are also performed at Visit 4a and 5a. Laboratory tests will be classified as clinically significant or not clinically significant.

All laboratory tests including pregnancy testing will be listed for Safety Population.

7.4 Vital Signs

All vital signs throughout the clinical trial will be measured in a rested (5 minutes) and seated position. Blood pressure, heart rate, respiratory rate, and oral temperature will be measured at the Medical Screening Visit, the Pre-Treatment Period (Visits 2a, 2b, and 2c), the Randomization Visit (Visit 3), the Post-Treatment Periods 1 and 2 (Visits 4a, 4b, 5a, and 5b), and any ETV.

Observed vital signs and changes from baseline (the last non-missing assessment prior to the first dose of ADX-629 or placebo) for vital signs will be summarized over visit by treatment. Baseline is defined as the last non-missing measurement taken prior to the first dose.

Listings will be provided for the Safety Population.

7.5 12-Lead ECG

A 12 lead ECG will be recorded at the Screening Visit and 1 hour (± 15 min) post dose at Visit 3, Visit 4a, and Visit 5a. Additional ECGs may be obtained at the discretion of the Investigator(s) or designee.

ECG will be listed for the Safety Population.

7.6 COVID-19 Test (SARS-CoV-2)

Within 5 days of study Visits 2a, 4a, and 5a, a nasal/nasopharyngeal/oropharyngeal swab will be

collected at the clinical site for SARS-CoV-2 testing. Subjects with a positive test result will be withdrawn from the study.

COVID-19 testing results will be listed for the Enrolled Population.

8. Efficacy Analyses

All efficacy endpoints will be summarized for the Intent-to-Treat Population. Sensitivity analysis will be performed on the Per-Protocol Population.

All efficacy data will be listed for the Safety Population.

8.1 Forced Expiratory Volume in One Second (FEV1) Following Allergen Challenge

FEV1 measurement is reported in litres. Normal values for FEV1 vary according to age, sex, height, weight, and ethnicity. To account for such variations, predicted FEV1% will be calculated. Predicted FEV1% is defined as subject's FEV1 value expressed as a percentage of the reference average FEV1 for a person of similar age, sex, and body composition.

Observed and changes from baseline (pre-saline within the visit) over time points as follows during post-BAC assessment (Visits 4a and 5a) for FEV1% will be summarized by treatment:

- Post-BAC (during 0-3 h) (the Key Efficacy Endpoint is change from baseline)
- Post-BAC (during 3-7 h)

The difference between treatments of mean predicted FEV1% change from baseline at each time point from 0 to 3 hours will be calculated along with the 2-sided 95% CI and the associated p-value from the MMRM model.

If 3 or more predicted FEV1% change from baseline over all time points from 30 to 180 minutes (in aggregate) of ADX-629 minus placebo is > 0 , and corresponding p-value of the contrast is < 0.05 , then the Key Efficacy Endpoint will be achieved.

If the model does not converge after fitting different covariance matrices, to compare treatment groups, a paired t-test based on averaged values across all timepoints (ignoring the correlation within subjects) will be provided.

The following plots will be provided for Intent-to-Treat Population:

- Spaghetti plots of the difference of predicted FEV1% (ADX-629 minus vehicle) over time
- Mean and mean changes of the difference of predicted FEV1% (ADX-629 minus vehicle) from baseline over time
- Difference of changes in least square means from the MMRM model over time

In addition, area under curve (AUC) over 0-3 hours post-BAC, 3-7 hours post-BAC, and 0-7 hours post-BAC will be summarized. To be included in the 0-3-hour AUC analysis, subjects must have non-missing data at baseline and non-missing data from at least three other timepoints. To be included in the 3-7-hour AUC analysis, subjects must have non-missing data at 3 hours and non-missing data from at least three other timepoints. To be included in the 0-7 hour AUC analysis, subjects must have non-missing data at baseline and satisfy all other conditions for the 0-3-hour and 3-7 hour AUC analyses.

8.2 Sputum Analysis

- Sputum is induced, collected, and processed at following timepoints: Approximately 7 hours post-BAC (Visit 2b, Visit 4a and Visit 5a), and
- Approximately 24 hours post-BAC (Visit 2c, Visit 4b and Visit 5b).

Observed and changes of absolute count and percentage (%) of leukocyte counts of sputum eosinophils and neutrophils from baseline (Visit 2b) at 7 hours post-BAC during the treatment periods (Visits 4a and 5a) will be summarized.

A similar analysis will also be performed at 24 hours post-BAC using the last non-missing assessment at Visit 2c as baseline.

P-values for comparison of changes from baseline between treatments at 7 hours and 24 hours, and comparison of change from baseline from 7 hours to 24 hours, will be provided using the paired t-test and the Wilcoxon signed-rank test.

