3.2 Study Endpoints

- Safety Endpoint
 - Adverse events (AEs) and serious adverse events (SAEs)
- Efficacy Endpoints
 - Change from baseline (within visit) in forced expiratory volume in one second (FEV1) to post-BAC (during 0-3 h post-BAC [Key Efficacy Endpoint] and 3-7 h post BAC)
 - Absolute count and percentage differential count of sputum eosinophils and neutrophils at approximately 7 h and 24 h post-BAC
 - Allergen-induced shift in airway hyper responsiveness (AHR) as assessed by Methacholine PC20 (Mch PC20) post-BAC

- Change from baseline in fractional exhaled Nitric Oxide (FeNO) at approximately 7 h and 24 h post-BAC
- Exploratory Endpoints
 - Biomarkers (RASP and endotoxin-induced cytokine release) pre-BAC (at approximately 1 hour post-dose) and 7 h post-BAC
 - Area under curve (AUC) of FEV1 during 0-3 h post-BAC and/or 3-7 h post BAC

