4. DEFINITIONS AND CONVENTIONS FOR DATA HANDLING

4.1 Handling of Missing Data

Generally, imputation of missing data will not be performed.

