8.5 Asthma Control Questionnaire (ACQ)

The ACQ has 7 questions. It includes the 5 most important symptoms, one question about rescue bronchodilator use and one about FEV1 % predicted. Patients recall their experiences during the previous 7 days and respond to each of the first 6 questions using a 7-point scale (0 = totally controlled to 6 = extremely poorly controlled). The seventh question, concerning FEV1 % predicted, is completed by clinic staff.

The overall ACQ score is calculated as the mean of the response to all 7 questions. An ACQ score of 1.50 or greater indicates that a subject has inadequate asthma control.

The ACQ score and change from baseline (the last non-missing assessment at Visit 2a) and adequate of asthma control will be summarized over time. Subjects who didn't complete all 7 questions will be excluded from analysis. The inadequate asthma rate between treatments will be tested using Fisher's exact test and the overall ACQ score and change from baseline between treatments at Visit 4a/5a will be tested by paired t-test and Wilcoxon signed-rank test.

Listings will be provided for the Safety Population.

9. Appendix

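### SAP 8.2 tests sputum as change from one untreated baseline shared by both treatments; the baseline cancels from the paired tests at 7 h and 24 h and can only cost pairs when it is missing

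*SAP*

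**What the plan says.** SAP 8.2 defines the 7 h changes "from baseline (Visit 2b) at 7 hours post-BAC during the treatment periods (Visits 4a and 5a) will be summarized". For the later time point it adds: "A similar analysis will also be performed at 24 hours post-BAC using the last non-missing assessment at Visit 2c as baseline". Visits 2b and 2c both fall in the pre-treatment period, before randomization and the first dose at Visit 3 (Protocol 11.3 and 11.4). Each subject therefore has one untreated value per time point, and it serves both treatment periods.

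The tests are specified for the changes: "P-values for comparison of changes from baseline between treatments at 7 hours and 24 hours" "will be provided using the paired t-test and the Wilcoxon signed-rank test". No covariate or period term is named. Observed values are summarized alongside the changes, but no between-treatment p-value is specified for them.

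The listed endpoint is the post-challenge value itself (SAP 3.2; Protocol 7.2 agrees): "Absolute count and percentage differential count of sputum eosinophils and neutrophils at approximately 7 h and 24 h post-BAC". On missing data, SAP 4.1 says "Generally, imputation of missing data will not be performed". The ITT population in SAP 5.3 requires randomization and receipt of both treatments, and does not require a sputum baseline.

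**The concern.** In a crossover, each subject supplies a value on each treatment, and the paired tests use only the difference between them. Subtracting the same number from both values cannot alter that difference. It can only make the difference uncomputable when the subtracted number is absent.

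As written, a subject contributes to the 7 h test only with three usable samples (Visits 2b, 4a and 5a), and to the 24 h test only with three others (Visits 2c, 4b and 5b). Two of the three carry all the treatment information. With about 12 pairs planned, each avoidable loss matters for power and for the width of the confidence interval.

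**Working it through.** **Inputs**
- 12 subjects, 6 per sequence (SAP 2.3.1).
- Two-sided tests at 0.05 (SAP 6.1).
- Difference 0.1 and SD 0.1, stated for FEV1 (SAP 2.2, Protocol 14.2). The documents give no such figures for sputum. The ratio, a standardized difference d = 1, is borrowed for illustration.
- Number of missing baselines m, or sample failure rate f: not in the documents. The ranges below are assumptions.

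**Step 1: the plan's own figure.** Read 0.1 as the SD of the within-subject difference. The paired t-test then has noncentrality d√n = 1 × √12 = 3.46 on 11 df, and power 88.3%. This agrees with the stated figure of more than 80%. (If 0.1 were instead the within-subject SD, the SD of the difference would be 0.1 × √2 = 0.141 and power 60.8%, so the first reading is the one that fits.)

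**Step 2: cancellation.** For one subject at one time point, let A be the value on ADX-629, P the value on placebo and B the shared baseline. Then

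(A − B) − (P − B) = A − P.

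Both planned tests are functions of these differences only. In 2,000 simulated skewed data sets of 12 subjects, the t-test p-values with and without B differed by at most 1e-15 (rounding error), and the signed-rank p-values did not differ. The identity holds for simple differences, which is how SAP 8.2 reads, and for differences of logs. It would not hold for percent change.

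**Step 3: only baselines missing.** The change-based test keeps n = 12 − m pairs; the observed-value test keeps 12. At d = 1:

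| Baselines missing | Pairs, change | Power, change | Power, observed | CI width, change ÷ observed |
|---|---|---|---|---|
| 0 | 12 | 88.3% | 88.3% | 1.00 |
| 1 | 11 | 84.7% | 88.3% | 1.06 |
| 2 | 10 | 80.3% | 88.3% | 1.13 |
| 3 | 9 | 74.8% | 88.3% | 1.21 |
| 4 | 8 | 68.1% | 88.3% | 1.32 |

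The width ratio is (t on n − 1 df ÷ √n) ÷ (t on 11 df ÷ √12), at equal SD.

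**Step 4: any sample may fail.** Suppose every sample fails independently with probability f. Expected pairs are 12(1 − f)² for observed values and 12(1 − f)³ for changes. Power is averaged over the binomial number of pairs:

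| f | Pairs, observed / change | Power at d = 1, observed / change | Loss at d = 1 | Loss at d = 0.5 |
|---|---|---|---|---|
| 5% | 10.8 / 10.3 | 83.6% / 80.9% | 2.6 points | 1.6 points |
| 10% | 9.7 / 8.7 | 77.8% / 71.8% | 6.1 points | 3.0 points |
| 20% | 7.7 / 6.1 | 63.9% / 50.6% | 13.3 points | 4.6 points |

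Losses were computed before rounding the powers.

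**Step 5: the other comparison in the same sentence.** SAP 8.2 also plans a comparison from 7 h to 24 h. Within one treatment, with Y the on-treatment value, this is (Y24 − B2c) − (Y7 − B2b) = (Y24 − Y7) − (B2c − B2b). The two baselines are different samples and do not cancel, so Step 2 does not apply there.

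**The case against.** The strongest reply is that the harm is conditional. If every randomized subject has both baseline samples, the two analyses give the same p-values. The documents state no sputum failure rate, several inclusion criteria are redacted, and eligibility is reviewed again at Visit 3. Whether a subject without baseline sputum could be randomized at all cannot be determined. This stands.

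The size is also uncertain. Step 4 assumes independent failures. If failures cluster within subjects, those lacking a baseline would often lack an on-treatment sample too and be lost under either analysis, so the extra loss would be smaller. It is also smaller at d = 0.5. Both limits stand.

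A reader might infer that the SAP has an explicit rule excluding subjects without a sputum baseline. It does not. SAP 8.1 writes such rules for the FEV1 AUC; SAP 8.2 has none, and SAP 4.1 is qualified as a general rule. The loss is inferred from a paired test on changes with no imputation and no fallback. Affected subjects would stay in the ITT population, the observed-value summaries and the listings, and would drop only from the p-value at the time point concerned.

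A reader might also extend the point to the asthma control questionnaire, where the Visit 2a baseline is shared too. SAP 8.5 says "the overall ACQ score and change from baseline between treatments at Visit 4a/5a will be tested by paired t-test and Wilcoxon signed-rank test". Because the score itself is already tested, a missing Visit 2a value removes no pair from that test. What remains is a duplicate p-value, which is not part of this point. Nor does the point reach FeNO (SAP 8.4), whose baseline is taken anew in each period and does not cancel.

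Finally, sputum is not the key efficacy endpoint and safety is the primary objective. That limits the weight of the point, but does not affect the algebra.

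**Conclusion.** The point holds as an efficiency improvement to SAP 8.2, confined to the between-treatment tests at 7 h and 24 h. The shared baseline contributes nothing to either test and can only remove pairs.

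With complete baselines the cost is nil. With 1 to 4 of 12 baselines missing and nothing else missing, power falls from 88% to between 85% and 68%. These figures assume a standardized paired effect of 1 taken from the FEV1 sizing and a number of missing baselines that the documents do not give. Under independent failure of 5% to 20% of samples, the loss is 2.6 to 13.3 points at that effect and 1.6 to 4.6 points at half of it.

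The documents do not support reading this as bias or an invalid test. The planned comparison is valid for the subjects it retains, and moving it to observed values also matches the endpoint as listed.

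**What to change.** In SAP 8.2, specify that the between-treatment paired t-test and signed-rank test use the observed post-challenge values: Visit 4a against Visit 5a for 7 h, and Visit 4b against Visit 5b for 24 h, each assigned to its treatment. Include all ITT subjects with both values at that time point. Keep change from Visit 2b or 2c as a descriptive summary. Leave the separate 7-to-24 h comparison as planned.

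The cost is a wording change before database lock, with no new data. With complete baselines the p-values are identical; otherwise the change can only retain pairs.

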8.3 Allergen-Induced Shift in Airway Hyper-Responsiveness

At Visits 2a, 4b, and 5b, subjects will undergo methacholine challenge testing (MCT). At Visit 2a, subjects will undergo bronchoprovocation challenge with progressively increasing concentrations of methacholine (Mch) to determine the baseline provocation concentration of inhaled methacholine required to reduce FEV1 by 20% (PC₂₀). The PC₂₀ concentration will then be

administered to assess FEV1 and predicted FEV1 % at Visits 4b and 5b.

Following the Mch PC₂₀ exposure, FEV1 (and predicted FEV1%) and change from within-visit baseline (post-saline/baseline timepoint at Visits 4b and 5b) will be summarized by treatment. In addition, time to return to 10% of baseline after Mch administration will be summarized by treatment.

P-values for comparison of changes from baseline between treatments will be provided using the paired t-test and the Wilcoxon signed-rank test.

8.4 Fractional Exhaled Nitric Oxide (FeNO)

FeNO will be measured at Visit 4a, 4b, 5a and 5b at following timepoints:

- Pre-BAC at Visit 4a and Visit 5a (baseline)
- Approximately 7 hours post BAC at Visit 4a and Visit 5a
- Approximately 24 hours post BAC at Visit 4b and Visit 5b.

Observed and changes from baseline (pre-BAC assessment at Visit 4a or 5a) at approximately 7 hours and 24 hours post BAC will be summarized.

P-values for the comparison of treatment groups at 7 hours and 24 hours, and comparison of change from baseline from 7 hours to 24 hours, will be provided using the paired t-test and the Wilcoxon signed-rank test.

8.5 Asthma Control Questionnaire (ACQ)

The ACQ has 7 questions. It includes the 5 most important symptoms, one question about rescue bronchodilator use and one about FEV1 % predicted. Patients recall their experiences during the previous 7 days and respond to each of the first 6 questions using a 7-point scale (0 = totally controlled to 6 = extremely poorly controlled). The seventh question, concerning FEV1 % predicted, is completed by clinic staff.

The overall ACQ score is calculated as the mean of the response to all 7 questions. An ACQ score of 1.50 or greater indicates that a subject has inadequate asthma control.

The ACQ score and change from baseline (the last non-missing assessment at Visit 2a) and adequate of asthma control will be summarized over time. Subjects who didn't complete all 7 questions will be excluded from analysis. The inadequate asthma rate between treatments will be tested using Fisher's exact test and the overall ACQ score and change from baseline between treatments at Visit 4a/5a will be tested by paired t-test and Wilcoxon signed-rank test.

Listings will be provided for the Safety Population.

9. Appendix

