10.2 Randomization Sequence

At Visit 3, eligible subjects will be randomized to one of the two sequences shown below. The randomization will be generated in blocks of two with each sequence occurring once in each block.

The randomization schedule will be generated by using SAS® statistical software (Version: 9.4 or higher; SAS Institute Inc., USA). The randomization schedule will be generated by a biostatistician of [REDACTED] Limited.

The randomization schedule will be maintained under controlled access. The personnel involved in the dispensing of investigational products will be accountable for ensuring compliance to the

randomization schedule. The analytical staff concerned will not have access to the randomization schedule during the course of analysis.

Treatments will be administered according to a two-treatment, two-period, and two-sequence design.

	Period 1	Period 2
Sequence 1	A	B
Sequence 2	B	A

Number of subjects per sequence = 6

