14.4.4 Statistical Analysis of Efficacy Data

Generally, the key efficacy variable may be analyzed using a mixed effect model for repeated measures. The following terms may be included in the model:

- sequence, visit (i.e., period), treatment group, post-BAC assessment time as independent factors, interaction of treatment by post-BAC assessment time
- subject as random effect
- Baseline within each visit as covariate
- If deemed appropriate, additional covariates for FEV1: baseline sputum eosinophil count

AUCs may be analyzed using a mixed effect model with following terms:

- sequence, visit (i.e., period), treatment group
- subject as random effect

Baseline assessment for each period (within visit) will be defined in the SAP.

The other efficacy endpoints may be compared between treatments using appropriate statistical models.

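### SAP 8.5 tests a paired yes/no ACQ outcome with Fisher's exact test, and the key-endpoint fallback and the paired tests in SAP 8.2 to 8.5 leave out period

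*SAP*

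**What the plan says.** Protocol 10.2 sets the design: "Treatments will be administered according to a two-treatment, two-period, and two-sequence design", with six subjects planned per sequence. SAP 5.3 limits the ITT population, used for efficacy, to randomized subjects who received both treatments.

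SAP 8.5 splits the ACQ score at 1.50 and states: "The inadequate asthma rate between treatments will be tested using" Fisher's exact test. The sentence goes on to say that the "overall ACQ score and change from baseline between treatments at Visit 4a/5a will be tested by paired t-test and Wilcoxon signed-rank test".

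The other tests are:

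- **Key-endpoint fallback (SAP 8.1).** If the MMRM does not converge, "a paired t-test based on averaged values across all timepoints (ignoring the correlation within subjects) will be provided".
- **Sputum (SAP 8.2).** P-values "will be provided using the paired t-test and the Wilcoxon signed-rank test". The 7 h baseline is Visit 2b. The 24 h analysis is done "using the last non-missing assessment at Visit 2c as baseline".
- **Methacholine (SAP 8.3).** "P-values for comparison of changes from baseline between treatments will be provided using the paired t-test and the Wilcoxon signed-rank test".
- **FeNO (SAP 8.4).** The same two tests.

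None of these has a period or sequence term. Protocol 14.4.4 lists for the key endpoint "sequence, visit (i.e., period), treatment group, post-BAC assessment time as independent factors", and gives sequence, period, treatment and random subject for AUC. For the other efficacy endpoints it names no model. The protocol's Study Summary gives the SAP precedence on statistical matters.

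**The concern.** **Fisher's test.** The two inadequate-control rates come from the same people. Fisher's test treats them as two independent groups of 12 and ignores which subjects changed category between treatments. SAP 8.5 thus handles one measurement as paired when it is a score and as unpaired when it is dichotomised.

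**Period.** Visits 4a/4b and 5a/5b are about three weeks apart, after repeated allergen challenges. A paired t-test or signed-rank test counts any shift between periods as noise and, if the sequences end up unequal, mixes part of it into the treatment estimate. Exposure differs by endpoint:

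- FEV1, methacholine response and FeNO use a within-visit baseline, which removes a shift in level.
- Sputum and ACQ use one pre-treatment baseline (Visits 2b/2c and 2a). It cancels from the difference between treatments, so a shift in level between Visits 4 and 5 stays in.

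**Wording.** The bracketed phrase in the fallback is unclear, because a paired test exists to use within-subject correlation.

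At stake is power in listed efficacy endpoints with about 12 subjects, and an ACQ p-value that does not have its stated meaning.

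**Working it through.** **1. The plan's own power figure.** Inputs from Protocol 14.2 and SAP 6.1: n = 12, difference 0.1, SD 0.1, two-sided alpha 0.05. Reading 0.1 as the SD of the paired difference (the documents do not say), the noncentrality is √12 × 0.1/0.1 = 3.46. With 11 df, power is 0.883, which agrees with the stated figure of more than 80%. Two independent groups of 6 would give 0.347. The design's power depends on the pairing.

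**2. How the pairing changes the ACQ p-value.** Let b and c be the numbers inadequate on one treatment only. Exact McNemar: p = 2·P(X ≤ min(b,c)), with X ~ Bin(b+c, ½). Mid-p subtracts P(X = min(b,c)).

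| Margins | Discordant | Fisher | Exact McNemar | Mid-p McNemar |
|---|---|---|---|---|
| 7/12 v 2/12 | 5:0 | 0.089 | 2 × (½)⁵ = 0.0625 | 0.0625 − 0.03125 = 0.031 |
| 9/12 v 3/12 | 6:0 | 0.039 | 0.031 | 0.016 |
| 9/12 v 3/12 | 9:3 | 0.039 | 0.146 | 0.092 |
| 5/12 v 0/12 | 5:0 | 0.037 | 0.0625 | 0.031 |

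At 9/12 v 3/12 Fisher gives the same answer for two quite different sets of paired data.

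**3. Size and power, 12 pairs, all tables enumerated.** The rates p₁, p₂ and the within-subject correlation phi are assumptions. The probability of being inadequate on both is p₁p₂ + phi·√(p₁(1−p₁)p₂(1−p₂)).

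- Fisher size at equal rates of 0.3: 0.017, 0.005 and 0.001 for phi 0, 0.3 and 0.5 (nominal 0.05).
- Largest size of mid-p McNemar at n = 12: 0.046.

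| Rates, phi 0.3 | Fisher | Exact McNemar | Mid-p McNemar | Prescott mid-p | Mainland-Gart |
|---|---|---|---|---|---|
| 0.1 v 0.5 | 0.40 | 0.33 | 0.55 | 0.57 | 0.16 |
| 0.1 v 0.3 | 0.06 | 0.03 | 0.09 | 0.10 | <0.01 |
| 0.05 v 0.2 | 0.024 | <0.01 | 0.031 | 0.035 | <0.01 |

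**4. Period omitted, six per sequence.** Let d be a subject's difference (ADX-629 minus placebo) with SD σ, τ the treatment effect and π the period effect. Then E(d) = τ + π in sequence AB and τ − π in BA. The mean of d is still τ, but the expected sample variance becomes σ² + π²·n/(n−1). At π = 1σ that is 1 + 12/11 = 2.09σ². Simulation, with power at τ = 1σ:

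| π (assumed) | Paired-t size | Paired-t power | Power with period | Signed-rank power | Rank-sum on period differences |
|---|---|---|---|---|---|
| 0 | 0.050 | 0.88 | 0.88 | 0.85 | 0.83 |
| 0.25σ | 0.044 | 0.87 | 0.88 | – | – |
| 0.5σ | 0.030 | 0.82 | 0.88 | 0.77 | 0.83 |
| 1σ | 0.006 | 0.62 | 0.88 | 0.52 | 0.83 |

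**5. Unequal sequences.** E(mean d) = τ + π(n₁ − n₂)/n. The bias is π/11 = 0.09π at 6:5, 2π/12 = 0.17π at 7:5 and 2π/10 = 0.20π at 6:4.

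**6. Cost of the period term.** With no period effect, noncentral-t power goes from 0.883 (11 df) to 0.876 (10 df).

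**The case against.** - **Fisher's weight.** ACQ control is not a listed endpoint in either document, and in these enumerations Fisher carries no extra false-positive risk. Subjects enter with mild controlled asthma, so rates such as 0.5 may be unrealistic; at 0.1 v 0.3 or below no test has useful power. The 7/12 v 2/12 example uses the pairing most favourable to McNemar: with discordant 6:1 or 7:2 the mid-p value is 0.070 or 0.109. All of this stands and limits the weight, but none of it makes an independent-groups test right for paired data.
- **No contradiction for most endpoints.** Protocol 14.4.4 says its models may be used, and gives period terms only for the key endpoint and AUC. For sputum, methacholine and FeNO the omission is a weakness, not a conflict. This stands. Only the fallback drops terms that the protocol names for that endpoint, and it applies only if the MMRM fails.
- **Small, conditional harm.** At 0.25 SD the loss is 0.01 in power, and a 1 SD period effect is as large as the assumed treatment effect. With unequal sequences the paired t-test stays below 0.05 at 7:5 and 6:4 (0.036 and 0.037 at 0.5 SD); at 8:4 it reaches 0.055. So the concern is lost power and a biased estimate, with little type I error inflation.
- **Fewer listed endpoints exposed.** Within-visit baselines protect methacholine and FeNO from level shifts, which leaves mainly sputum. They do not remove a change between periods in the response to challenge itself. The listed methacholine endpoint is also PC20, while SAP 8.3 tests FEV1 change.
- **The bracketed phrase** may mean only that averaging ignores correlation across timepoints. That is plausible, but the text does not say so.

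**Conclusion.** The concern holds. Fisher's exact test in SAP 8.5 is wrong for the design, and nothing elsewhere in the documents corrects it. The usual consequence is a test far below its nominal size. The power gain from a suitable paired test is worthwhile at large differences (0.40 to 0.55 at 0.1 v 0.5) and slight at low rates.

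Leaving out period is not an error when the sequences are equal and there is no period effect. Otherwise it costs power (0.88 to 0.82 at 0.5 SD, 0.62 at 1 SD) and, with unequal sequences, biases the estimate. Sputum is the most exposed listed endpoint; the key-endpoint fallback matters if it is used. Unequal sequences are plausible, since a positive COVID-19 test leads to withdrawal and ITT requires both treatments.

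The ACQ rates, phi, period effects and imbalances are assumptions; the documents give none. This should be changed before database lock, but it does not threaten the trial.

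**What to change.** Changes to the SAP:

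1. **ACQ inadequate-control rate (8.5).** Replace Fisher with mid-p McNemar, or with Prescott's test (mid-p) if period is to be allowed for. Name one in advance. Exact McNemar and Mainland-Gart are poor choices as the main test, because both have less power than Fisher at this sample size.
2. **Sputum, FEV1 change after methacholine, FeNO, ACQ score and the 8.1 fallback on averaged values.** Use a mixed model with sequence, period, treatment and random subject, as Protocol 14.4.4 gives for AUC.
3. **Non-parametric version.** Replace the signed-rank test with the rank-sum test comparing period differences between sequences.
4. **Fallback wording (8.1).** Delete the bracketed phrase about within-subject correlation, or state which correlation is meant.

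The cost is SAP wording and one degree of freedom. With no period effect, power moves from 0.883 to 0.876 for the t-test and from 0.85 to 0.83 for the rank version. No data collection or trial procedure changes.
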